4.2 Baseline practice, practice staff, and patient characteristics

Baseline practice and practice staff characteristics include:

- State (Victoria, Tasmania)
- IRSD terciles based on the Index of Relative Socio-Economic Disadvantage (IRSD) ⁸ using the practice postcode. The first tercile represents relatively disadvantaged sociodemographic geographic areas compared to geographic areas with higher ranks (Tercile 3).
- Practice participation in a formalised QI program in the past 6 months (yes, no)

- Practice size based on the GP full-time equivalent (FTE) of 4 or less FTE or greater than 4 FTE as reported by the practice. FTE will be defined as the total number of full-time GPs plus the total number of part time GPs multiplied by 0.5FTE.
- GPs sex (male, female)
- GPs age group (<35 years; 35 to 50 years; >50 years)
- Number of FTE registered nurses. FTE will be defined as the total number of full-time nurses plus the total number of part time nurses multiplied by 0.5FTE.
- Registered nurses' sex (male, female)
- Registered nurses age group (<35 years; 35 to 50 years; >50 years)
- Number of FTE practice managers and administrative staff. FTE will be defined as the total number of full-time practice managers/administrative staff plus the total number of part time practice managers/administrative staff multiplied by 0.5FTE.
- Practice managers/administrative staff sex (male, female)
- Practice managers/administrative staff age group (<35 years; 35 to 50 years; >50 years)

Patient characteristics and medication prescribed, observations and/or pathology test results recorded at baseline (4th October 2021) extracted from the EMR include:

- Sex (male, female, other)
- Age (years)
- ACEI/ARB prescription status (ACEI only, ARB only, both ACEI/ARB, None)
- Statin prescription status (yes/no)
- Recommendation for guideline concordant care to consider initiating medications (Statin only; ACEI/ARB only; Both statin and ACEI/ARB)
- Systolic blood pressure (mmHg)
- Total cholesterol (mmol/L)
- LDL cholesterol (mmol/L)
- HDL cholesterol (mmol/L)
- Triglycerides (mmol/L)
- uACR (mg/g)
- eGFR (ml/min/1.73²)
- CVD risk category (low, medium, and high)
- Recorded diagnosis of type 2 diabetes prior to baseline (yes/no)

4.3 Other information extracted from the EMR that occur during the trial period

- Patient experienced ischemic stroke, heart attack, peripheral vascular disease, and/or kidney dialysis
- Pregnancy
- Patient deceased
- Time between most recent reported measurement at end of the trial in the EMR compared to baseline for secondary outcomes (1 to 8)

4.4 Withdrawal and Follow-up

Staff within practices and/or the practice may withdraw at any time. If a practice withdraws then no further patient data will be extracted from the EMR system. However, existing data (prior to notice of withdrawal) will be used in the final analysis unless the practice requests existing data also be excluded. Individual patients can also withdraw their data by notifying their general practice that they no longer consent to their data being used for research purposes. As the intervention is applied at the general practice level within the EMR system this means that no further patient data will be extracted. However, existing data (prior to notice of withdrawal) will be used in the final analysis unless the participant requests existing data also be excluded.

4.5 Descriptive analysis

The flow of practices and eligible patients from recruitment to trial end, will be shown in a CONSORT diagram¹, see Appendix Figure 1 for the template. The report will include the number of practices approached for involvement in the trial, the number of practices that met study eligibility criteria, the number practices consented and randomised by their allocated study arm, together with the total number and the mean number of eligible patients per practice and number that were included in the intention to treat analysis. The number of practices and/or patients who withdraw or discontinue will also be summarised by study arm and period that the withdrawal/discontinuation occurred (0-6 months, 7-9 months, 10-12 months). When such information is available, the reason a practice/patient withdrew or discontinued the intervention will be reported by study arm.

Descriptive statistics will be used to describe general practice and patients' baseline characteristics and baseline outcome measures overall and by study arm as outlined in Appendix B Table 1 and Table 2. Descriptive statistics will also be used to summarise other information extracted from the EMR that occur during the trial period by study arm and overall. Categorical data will be summarised using counts and percentages, according to the number of eligible patients with available data. Continuous data will be summarised using arithmetic mean, standard deviation if the data have a symmetric distribution. When appropriate, continuous outcome data with a right skewed distribution may be presented as a geometric mean instead of an arithmetic mean. Otherwise, if the distribution if the data is non-symmetrical, the median and interquartile range (25th and 75 percentiles) will be presented instead. The intra-cluster correlation coefficient with 95% intervals will also be reported for baseline patient measurements estimated using one-way analysis of variance.

4.6 Primary Analyses

The primary analyses will use an intention to treat (ITT) approach, where all practices randomised will be included in the analysis by their allocated study arm status, regardless of whether they received all, part, or none of the intended intervention.

4.6.1 Primary outcome

For the primary outcome, the odds ratio (relative measure) and the difference in proportions between the intervention and control arms (absolute measure) will be estimated using a generalised linear model (GLM) with the logit link and identity link functions, respectively, and binomial distribution for both models. Both models will include randomisation stratification factors, GP FTE and IRSD terciles as covariates, and use Generalised Estimating Equations with an exchangeable correlation structure and robust standard errors to allow for correlation of outcomes within general practice. If the model used to

estimate the risk difference fails to converge, the risk difference will be derived from the GLM with the logit link function.^{9,10}

Absolute (difference in proportions between the intervention and control arms), and relative (odds ratio) estimated intervention effects for the primary outcome will be reported with 95% confidence intervals and p-values.

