The FHT trial is a stratified head-to-head cluster randomised controlled trial. The unit of randomisation is the general practice, where practices are randomly allocated concurrently on 1:1 ratio to either participate in the FHT CKD QI module (intervention arm) or the FHT Cancer-risk module (active control arm for the CKD study). All general practices will be provided access to the respective QI programs at the commencement of the trial (October 4th, 2021). Please refer to the trial protocol for a detailed description of the intervention and comparator.

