3.1 Level of statistical significance and confidence intervals

Estimates of the intervention effect will be reported with 95% confidence intervals and two sided-p-values.

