4.6.2 Secondary outcomes

Statistical methods described for the primary outcome will be used for the **binary secondary outcomes 1, 2, and 6.** For each outcome, an additional covariate will be fitted in the regression model. For outcome 1, we will adjust for whether a recommendation would have been made to consider initiating ACEIs or ARBs for the patient (yes/no). Similarly for outcome 2, we will adjust for whether the recommendation would have been received to consider initiating statins (yes/no). For outcome 6, we will include uACR at baseline as a covariate.

For the analysis of continuous secondary **outcomes 3, 4, 5 and 8**, a mixed effects linear model with study arm, baseline measure of the outcome (where appropriate), randomisation stratification factors (GP FTE and IRSD terciles) will be fitted as fixed effects and general practice as a random effect. The estimated intervention effects will be reported as the difference in means between the intervention and active control arms with 95% confidence intervals and p-values.

Outcomes with a skewed distribution may be log-transformed, in which case, the estimated intervention effect will be reported as a ratio of the geometric means between study arms, with their respective 95% confidence interval and p-value.

Secondary outcome 7 will be analysed using the proportional odds logistic regression model with randomisation stratification factors (GP FTE and IRSD terciles) and baseline CVD risk group included as fixed effects. Generalised Estimating Equations with an exchangeable correlation structure and robust standard errors will be used to allow for correlation of outcomes within general practice. An alternative model will be considered if the assumption of proportional odds is not met.¹¹

The estimated intervention effect will be reported as a cumulative odds ratio with their respective 95% confidence interval and p-value.

Secondary outcome 9 will utilise a Poisson mixed effects model (or a Negative Binomial mixed effects model if overdispersion is detected), with fixed effects for study arm and the randomisation stratification factors (GP FTE and IRSD terciles), and random effect for general practice. The estimated intervention effect will be reported as differences in rate between the intervention and control arms and rate ratios with 95% confidence intervals and p-values.

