4.4.4 Primary outcome

For the primary outcome, the odds ratio (relative measure) and the difference in proportions between the intervention and control arms (absolute measure) will be estimated using a generalised linear model (GLM) with the logit link and identity link functions, respectively, and binomial distribution for both models. Both models will include randomisation stratification factors, GP FTE and IRSD terciles as covariates, and use Generalised Estimating Equations with an exchangeable correlation structure and robust standard errors to allow for correlation of outcomes within general practice. If the model used to estimate the risk difference fails to converge, the risk difference will be derived from the GLM with the logit link function.^{11,12}

The absolute (difference in proportions between the intervention and control arms) and relative (odds ratio) estimated intervention effects for the primary outcome will be reported with 95% confidence intervals and p-values.

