4.4.5 Secondary outcomes analysis

Statistical methods described in the primary outcome will be used for the **binary secondary outcomes 1-5.**

Secondary outcome 6 will utilise a Poisson mixed effects model (or a Negative Binomial mixed effects model if overdispersion is detected), with fixed effects for study arm and the randomisation stratification factors (GP FTE and IRSD terciles), and random effect for general practice. The estimated intervention effect will be reported as differences in rate between the intervention and control arms and rate ratios with 95% confidence intervals and p-values.

Secondary outcome 7 will be analysed using a time to event analysis to compare the time to investigation for patients in the open cohort with an altered test results identified as at risk of an undiagnosed cancer between the study arms using a Cox proportional hazards model, adjusted for the randomisation stratification factors (GP FTE and IRSD terciles). Robust standard errors will be used to adjust for clustering effect by general practice. The proportional hazards assumption will be assessed following a two-step procedure: (1) calculate covariate specific tests and (2) plot the scaled and smoothed scaled Schoenfeld residuals obtained from the model.¹³ Kaplan-Meier survival curves will also be used to present time to event by study arm¹⁴, and the overall survival data will be summarised following a stratified proportional hazards model or a parametric model as appropriate.¹³ A sensitivity analysis using a competing risk analysis will be considered if patients at risk of undiagnosed cancer have died prior to an investigation/end of the trial follow-up period.

Estimates of the intervention effect will be reported as hazard ratios and 95% confidence intervals and p-value.

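### Both plans base primary and binary secondary inference on GEE robust standard errors without stating a small-sample correction or reference distribution; unless practices are many, such a test rejects too often

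*SAP*

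**What the plan says.** The unit of randomisation is the practice: "practices are randomly allocated concurrently on 1:1 ratio" (CKD plan, section 2; the cancer-risk plan agrees).

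- **CKD primary outcome (4.6.1).** A logit model for the odds ratio and an identity-link model for the risk difference, both of which "use Generalised Estimating Equations with an exchangeable correlation structure and robust standard errors to allow for correlation of outcomes within general practice". On covariates: "Both models will include randomisation stratification factors, GP FTE and IRSD terciles as covariates".
- **Cancer-risk primary outcome (4.4.4).** The same specification: "use Generalised Estimating Equations with an exchangeable correlation structure and robust standard errors".
- **Binary secondary outcomes.** CKD section 4.6.2 opens "Statistical methods described for the primary outcome will be used for the" binary outcomes 1, 2 and 6, each with one added covariate. Cancer-risk section 4.4.5 does the same for outcomes 1 to 5.
- **Reporting (3.1 in both plans).** "Estimates of the intervention effect will be reported with 95% confidence intervals and two sided-p-values".

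Neither plan says whether the robust variance is corrected for the number of practices, which distribution the test statistic is referred to, or what happens if practices are few. Section 1.1 of each plan leaves the sample size calculation to the protocol.

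**The concern.** The robust (sandwich) variance is justified as the number of clusters grows. The number of patients does not help. Each practice's residual is shrunk by its own influence on the fit, so the variance is biased downward. It is also noisy when practices are few, and a normal reference ignores that noise. Every covariate in the primary model is at practice level, which makes the bias worse for a given number of practices.

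At stake is the error rate of the headline test in two separate trials, and of the binary secondary outcomes that inherit the method. The choice of variance estimator and degrees of freedom belongs in an analysis plan. It can also move a borderline result across 5%, so it should be fixed before results are seen.

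**Working it through.** The plans contain no figure to reproduce: no practice count, intra-cluster correlation (ICC) or power. The check is therefore a conditional one, over assumed ranges.

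**Inputs from the plans.** Two-sided 5% (from the 95% intervals); 1:1 by practice; logit GEE, exchangeable, robust standard errors; covariates arm, practice size (two levels, at or below 4 FTE versus above) and IRSD terciles.

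**Practice-level parameters.** Intercept 1 + arm 1 + practice size 1 + IRSD 2 = 5.

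**Size of the bias, roughly.** Let K be the total number of practices and h the leverage of a practice. The leverages sum to the number of parameters, so the mean of h is 5/K. With a correct working model the squared residual has expectation of about (1 − h) times its true value, so the standard error is too small by a factor of about √(1 − 5/K).

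- K = 20: √0.75 = 0.866. The effective critical value is 1.96 × 0.866 = 1.70, which a standard normal exceeds two-sided with probability about 9.0%.
- K = 40: √0.875 = 0.935; 1.96 × 0.935 = 1.83; about 6.7%.

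This is the bias alone. Noise in the variance estimate adds to it, so simulation is needed.

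**Simulation A.** Beta-binomial outcomes with no intervention effect, 6,000 trials per cell (Monte Carlo standard error √(0.05 × 0.95/6000) = 0.3 points at 5%). Three assumed sets of ICC, mean practice size, coefficient of variation (CV) of size and outcome proportion: 0.01/30/0.6/0.15, 0.03/50/0.6/0.20 and 0.05/100/0.8/0.30. True type I error in %, range over the three sets:

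| K | Uncorrected, z | Uncorrected, t(K−5) | Kauermann-Carroll, t(K−5) | Mancl-DeRouen, t(K−5) |
|---|---|---|---|---|
| 20 | 12.6-14.3 | 10.0-11.3 | 6.0-6.4 | 2.7-3.0 |
| 30 | 8.3-11.4 | 7.0-10.0 | 4.9-6.6 | 3.1-3.7 |
| 40 | 7.4-9.0 | 6.6-8.1 | 4.8-6.0 | 3.4-4.1 |
| 60 | 6.1-7.2 | 5.6-6.5 | 4.8-5.5 | 3.6-4.4 |
| 80 | 6.3-6.4 | 5.8-5.9 | 5.0 | 4.3 |
| 120 | 5.8-6.1 | 5.4-5.8 | 4.7-5.2 | 4.1-4.8 |

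Kauermann-Carroll multiplies each practice's residual by (1 − h)^(−1/2), and Mancl-DeRouen by (1 − h)^(−1). Multiplying the uncorrected variance by K/(K − 1) helps little: with z it gives 11.8-13.4% at 20 practices and 7.2-8.7% at 40.

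**Simulation B, run separately.** 4,000 trials per setting, allocation within the six practice-size by IRSD strata, mean 60 patients, ICC 0.05, proportion 0.30, size CV 0.4-0.8, robust variance with the K/(K − 1) factor and z: 10.9-12.6% at 20 practices, 7.8-9.2% at 30, 7.5-8.2% at 40, 6.6% at 60, 5.8-6.0% at 100. With Kauermann-Carroll and t(K−5): 5.9-6.1%, 5.1-5.8%, 5.4-6.1%, 5.0-5.1%, 4.9-5.0%.

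The two agree. The excess is about 2 to 4 points at 40 practices and about 1 point at 100-120. The t reference alone does not remove it at 20 to 40.

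**The case against.** Four objections deserve an answer.

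*The deciding number is not in view.* The excess runs from large at 20 practices to about one point at 100-120, and nothing in the document places this trial in that range. This stands. A reader might infer that the trial's intervals will miss their nominal coverage by a material amount; the document does not support that.

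*The plans do not say that the intervals are normal-theory or the variance uncorrected.* This also stands. Both readings come from silence, and the exact charge is that neither point is specified. The conclusion survives, because a t reference without a corrected variance still over-rejects at 20 to 40 practices.

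*The same weakness might be read into the other models.* The phrase "Robust standard errors will be used to adjust for clustering effect by general practice" in cancer-risk section 4.4.5 concerns the Cox model for time to investigation. The wording "Generalised Estimating Equations with an exchangeable correlation structure and robust standard errors will be used to allow for correlation" in CKD section 4.6.2 concerns the ordinal outcome 7. Neither model was tested, nor were the linear mixed models for CKD outcomes 3, 4, 5 and 8, so no finding is made on them.

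*The simulations do not cover every planned binary model.* Correct. They use the logit link and practice-level covariates only. The identity-link model and the patient-level covariates added for CKD outcomes 1, 2 and 6 were not simulated.

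None of this argues for leaving the choice open. The corrections differ (at 40 practices, 4.8-6.0% for Kauermann-Carroll against 3.4-4.1% for Mancl-DeRouen), so a choice made after seeing results could matter. Section 3.2 of each plan refers to practice recruitment in the past tense, so the count could have been used to fix or justify the choice.

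**Conclusion.** The point holds conditionally. Both plans rest the primary and binary secondary inference on GEE robust standard errors with no stated small-sample correction or reference distribution. If the analysis is run with the uncorrected sandwich and z, the logit GEE test at nominal 5% has a true error of about 11-14% at 20 practices, 7.4-9.0% at 40, 6.1-7.2% at 60 and about 6% at 100-120. These figures rest on assumed ICCs of 0.01-0.05, mean practice sizes of 30-100, size CVs of 0.4-0.8 and outcome proportions of 0.15-0.30. They apply to the logit model only.

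The inflation in this trial is not established, because the practice count is not given here. The case for change is that a named alternative brings the error close to nominal throughout the range at low cost.

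**What to change.** In CKD sections 4.6.1 and 4.6.2 and cancer-risk sections 4.4.4 and 4.4.5, state that the primary and binary secondary GEE models use the Kauermann-Carroll bias-corrected sandwich, with intervals and p-values from a t distribution on (practices minus 5) degrees of freedom. Count the practices that contribute to the analysis concerned. Keep the uncorrected result as supportive. If the risk difference is derived from the logit model, use the same corrected covariance matrix. In the simulated logit model this gives 4.9-6.6% at 30 practices, 4.8-6.1% at 40 and 4.7-5.5% from 60 upward.

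The cost is a few sentences, an added routine in the analysis code, and wider intervals. By the average-leverage approximation, the widening is (1 − 5/K)^(−1/2) times the ratio of the t to the normal quantile:

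- K = 40: 1.069 × (2.030/1.960) = 1.11, about 11% wider.
- K = 120: 1.022 × (1.981/1.960) = 1.03, about 3% wider.

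If the actual practice count is large, the correction changes little.

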4.6.2 Secondary outcomes

Statistical methods described for the primary outcome will be used for the **binary secondary outcomes 1, 2, and 6.** For each outcome, an additional covariate will be fitted in the regression model. For outcome 1, we will adjust for whether a recommendation would have been made to consider initiating ACEIs or ARBs for the patient (yes/no). Similarly for outcome 2, we will adjust for whether the recommendation would have been received to consider initiating statins (yes/no). For outcome 6, we will include uACR at baseline as a covariate.

For the analysis of continuous secondary **outcomes 3, 4, 5 and 8**, a mixed effects linear model with study arm, baseline measure of the outcome (where appropriate), randomisation stratification factors (GP FTE and IRSD terciles) will be fitted as fixed effects and general practice as a random effect. The estimated intervention effects will be reported as the difference in means between the intervention and active control arms with 95% confidence intervals and p-values.

Outcomes with a skewed distribution may be log-transformed, in which case, the estimated intervention effect will be reported as a ratio of the geometric means between study arms, with their respective 95% confidence interval and p-value.

Secondary outcome 7 will be analysed using the proportional odds logistic regression model with randomisation stratification factors (GP FTE and IRSD terciles) and baseline CVD risk group included as fixed effects. Generalised Estimating Equations with an exchangeable correlation structure and robust standard errors will be used to allow for correlation of outcomes within general practice. An alternative model will be considered if the assumption of proportional odds is not met.¹¹

The estimated intervention effect will be reported as a cumulative odds ratio with their respective 95% confidence interval and p-value.

Secondary outcome 9 will utilise a Poisson mixed effects model (or a Negative Binomial mixed effects model if overdispersion is detected), with fixed effects for study arm and the randomisation stratification factors (GP FTE and IRSD terciles), and random effect for general practice. The estimated intervention effect will be reported as differences in rate between the intervention and control arms and rate ratios with 95% confidence intervals and p-values.

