2.5 Timing of final analysis and outcomes assessment

Statistical analyses for the CKD study are planned to commence when the final data set is received late October 2022 and after the Statistical Analysis Plan has been uploaded to the Australian and New Zealand Clinical Trials Registry. Analysis for the cancer-risk study described in a separate SAP is planned to commence in 2023.

Primary and secondary outcomes will be assessed at the trial end date, 30th September 2022, approximately 12-months after the trial start date, 4th October 2021. Subsequent references to the trial period refer to this 12-month period. The outcomes at end of the trial will be based on their most recent

recorded medication prescribed, observations and/or pathology test results in the EMR within the trial period.

Baseline measures of the outcome and patient characteristics will be assessed at the trial start date (4th October 2021). The baseline measures of the outcomes for eligible patients will be based on the history of observations and/or pathology test results in the EMR in the preceding 12 months from the 4th of October 2021, except for systolic blood pressure which will be based on the preceding 6 months, and current medication status, which considers the entire history of prescribed medications.

3. Statistical Principles

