(9) The rate of general practice encounters per patient over the trial period. This will be calculated using total number of general practice encounters in the 12-month trial period of all eligible patients with a diagnosis or pathology results consistent with CKD at baseline divided by the total time they were observed in the trial. For each patient, time will be one year, calculated from the date the trial commenced (4th October 2021) to the end of the trial (30th September 2022), except for patients/practices that discontinued during the trial period, where time observed will be calculated from the 4th October 2021 to the date the patient(s) discontinued/withdrew.

Health economics outcomes are:

(10) The cost of the installation for the software program for QI, training, QI support and education. This will be calculated at the general practice level, using cost data collected by Health and Biomedical Informatics Centre (HABIC R²) who developed and provided technical support for the FHT software and the FHT investigators and research team who liaised with practices and facilitated the education sessions.

(11) Cost of primary care service utilisation per patient per year. These will be calculated based on Medicare items, Provider Charge, Schedule Fee, Patient Out of Pocket in the Medicare Benefits Schedule (MBS) data linked to patients in the Patron for the FHT evaluation.

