- (4) Proportion of eligible patients whose sex at birth is coded as male in the EMR in the closed and open cohort with one raised PSA that have been followed up according to Cancer Council Australia guidelines⁴ within the 12-month trial period. Relevant investigations include a repeat PSA test, free to total PSA percentage and/or referral to a urologist^{5,8}. The absence of any of relevant recorded investigation during the trial period will be considered equivalent to not being investigated.
- (5) Proportion of eligible patients in the closed and open cohorts that have a new recorded diagnosis of prostate, oesophageal, gastric, colorectal, endometrial, lung or ovarian cancer recorded in the general practice EMR within the 12-month trial period. The absence of any of recorded diagnosis during the trial period will be considered equivalent of no diagnosis being made.
- (6) The rate of general practice encounters per eligible patient over the 12-month trial period. This will be calculated using total number of general practice visits over the trial period of all eligible patients identified as at risk of an undiagnosed cancer in the closed cohort divided by the total time they were observed in the trial. For each patient, time will be calculated from the date the trial commenced (4th Oct 2021) to the end of the trial (30th September 2022). If the patient enters in the open cohort, the time observed will be calculated from the date they the trial to the end of the trial (30th September 2022). For patients/practices that discontinue during the trial period, time observed will be calculated from they entered the (namely, the 4th October 2021 for the closed cohort or date they first report of an abnormal test result for the open cohort) to the date the patient(s) discontinued/withdrew from the trial.

(7) Time to investigation for patients with abnormal pathology results identified as at risk of an undiagnosed cancer in the open cohort. This includes any investigation, treatment, review of symptoms or referrals as described in the primary outcome. Time to investigation will be defined as the number of days between the initial altered test result date and the first investigation (retesting, investigations, treatments, referrals and review of symptoms). Outcomes will be assessed at 12 months from baseline and patient records without follow-up action by this time will be censored.

Health economics outcomes are:

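### The encounter-rate models (CKD outcome 9, cancer-risk outcome 6) omit pre-trial attendance and so give up precision in a secondary outcome; the planned analysis is still valid

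*SAP*

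**What the plan says.** Section 4.1 of the CKD SAP defines outcome 9 as "The rate of general practice encounters per patient over the trial period", that is, encounters divided by time observed. Section 4.2 of the cancer-risk SAP defines outcome 6 in the same way: "The rate of general practice encounters per eligible patient over the 12-month trial period". Neither definition refers to a period before the trial.

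For CKD outcome 9 the model is fitted "with fixed effects for study arm and the randomisation stratification factors (GP FTE and IRSD terciles), and random effect for general practice" (4.6.2). Section 4.4.5 of the cancer-risk SAP repeats this: "Secondary outcome 6 will utilise a Poisson mixed effects model (or a Negative Binomial mixed effects model if overdispersion is detected"), with the same fixed and random effects.

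The other CKD outcomes in 4.6.2 are treated differently:

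- Outcomes 3, 4, 5 and 8 use "a mixed effects linear model with study arm, baseline measure of the outcome (where appropriate), randomisation stratification factors".
- Outcome 6: "For outcome 6, we will include uACR at baseline as a covariate".
- Outcome 7 has "baseline CVD risk group included as fixed effects".
- Outcomes 1 and 2 are adjusted for whether the patient would have been flagged for the drug class in question.

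On timing, section 2.5 of the CKD SAP says: "Baseline measures of the outcome and patient characteristics will be assessed at the trial start date (4th October 2021").

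**The concern.** CKD outcome 9 is the only clinical secondary outcome in the CKD SAP with no patient-level baseline covariate, and no reason is given. Its natural covariate is the same count in the year before. One would expect prior attendance to predict later attendance, both for patients (frequent attenders) and for practices (recall habits, and what is recorded as an encounter).

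Nothing else in either SAP fills this role. Sensitivity analysis 1 adds prior QI participation, age and sex (CKD 4.7.1.1), plus cohort type in the cancer-risk SAP (4.5.1). Prior encounters are also absent from the baseline lists (CKD 4.2, cancer-risk 4.3) and from the Table 2 templates. A chance imbalance between arms would be neither adjusted for nor visible to a reader.

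At stake is how precisely the trial can say whether either program changes the number of GP encounters. Practices are the randomised unit, so stable differences between practices can make up much of the standard error.

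**Working it through.** **Inputs.** The covariate lists come from the sections above. The SAPs state no power, encounter rate, intra-cluster correlation (ICC) or between-year correlation for this outcome, so there is no figure of the plan to reproduce. Every number below rests on assumed values.

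**Step 1: variance ratio for a comparison of practices.** Let m be patients per practice, and let ρ_b and ρ_w be the correlations between pre-trial and trial log rates at practice and patient level.

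Variance ratio (adjusted / unadjusted) = [ICC(1 − ρ_b²) + (1 − ICC)(1 − ρ_w²)/m] / [ICC + (1 − ICC)/m]

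If ρ_b = ρ_w = ρ, this reduces to 1 − ρ² whatever the ICC and m:

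| ρ | Variance ratio | Variance cut | SE ratio |
|---|---|---|---|
| 0.3 | 0.91 | 9% | 0.95 |
| 0.5 | 0.75 | 25% | 0.87 |
| 0.7 | 0.51 | 49% of SE² removed | 0.71 |

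For the last row, 1 − 0.51 = 0.49: the adjusted variance is 51% of the unadjusted variance, so the cut is 49%. The 51% figure is the variance that remains.

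**Step 2: which level matters.** Take ICC 0.05 and m = 50. The unadjusted variance is 0.05 + 0.95/50 = 0.069, of which 0.05/0.069 = 72% lies between practices. With ρ_w = 0.5 and ρ_b = 0.8, the adjusted variance is 0.05 × 0.36 + 0.019 × 0.75 = 0.03225, a ratio of 0.47. Over ICC 0.02 to 0.10 and m of 50 or 150 the ratio runs from 0.38 to 0.55. The practice-level correlation therefore largely decides the gain.

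**Step 3: simulation with no true effect.** 2,000 runs, 20 practices per arm, 100 patients each, mean 8 encounters, log-scale SD 0.25 between practices and 0.6 between patients, patient-level correlation 0.7. Log practice means were regressed on arm, with and without the pre-trial log mean.

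| Practice-level correlation | SD of log rate ratio, unadjusted | SD, adjusted | Variance cut |
|---|---|---|---|
| 0.3 | 0.080 | 0.079 | 1 − (0.079/0.080)² = 2.5% |
| 0.5 | 0.085 | 0.074 | 1 − (0.074/0.085)² = 24% |
| 0.8 | 0.081 | 0.052 | 1 − (0.052/0.081)² = 59% |

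Both estimators averaged about 0 in every setting. The unadjusted log rate ratio correlated 0.28 to 0.77 with the chance difference between arms in the pre-trial rate. After adjustment that correlation was about 0 (−0.05 to 0.03).

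**Step 4: power.** If an effect has 80% power unadjusted, adjusted power is Φ((0.84 + 1.96)/√(1 − ρ²) − 1.96): 0.836 at ρ = 0.3, 0.899 at 0.5 and 0.975 at 0.7. The 80% starting point is itself an assumption.

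**The case against.** A reader might infer that an existing difference in attendance would pass for an effect of the program, so that the rate ratio is biased. The documents do not support that. Practices are randomised, the stratification factors are in the model, and the practice random effect with its 95% confidence interval already allows for chance differences between practices. The simulation showed no systematic bias.

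A reader might also infer that both SAPs contradict themselves. In the CKD SAP the contrast is real but softer than it looks. Outcomes 3, 4, 5 and 8 are defined as changes from baseline and outcome 6 is computed from baseline uACR, so a baseline term follows from the definitions. Only outcome 7 is not built that way, and the term for 3, 4, 5 and 8 is qualified as applying where appropriate. Outcome 9 is defined over the trial period alone, and its model matches that. In the cancer-risk SAP there is no contrast, because outcomes 1 to 5 are adjusted for the stratification factors only.

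Availability of the data is inferred. After its general statement on baseline measures, section 2.5 of the CKD SAP names observations, pathology results and medication history, not encounters.

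The sizes are assumed, and the simulation is a practice-level regression, not the planned mixed model. It leaves out GP FTE and IRSD terciles, which may already absorb part of the between-practice variance.

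All of this stands. It limits the point to efficiency in a secondary outcome. It does not remove the point, because no other planned analysis uses prior attendance.

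**Conclusion.** The point holds as a cheap improvement, not as the correction of an error. The planned encounter-rate analyses are valid. They give up precision and leave chance imbalance in prior attendance uncorrected in one secondary outcome of each study.

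With equal patient- and practice-level correlations, the adjusted variance is 91%, 75% and 51% of the unadjusted variance at correlations of 0.3, 0.5 and 0.7. These are cuts of about 9%, 25% and 49%; the figure of 51% at 0.7 is what remains, and should be read so wherever it is cited. At a practice-level correlation near 0.3 the simulated gain was negligible. The documents support no particular value, so none of these sizes is a prediction for this trial.

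**What to change.** In 4.6.2 (CKD) and 4.4.5 (cancer-risk), add each patient's encounter count from 4 October 2020 to 3 October 2021 to the Poisson or negative binomial mixed model, for example as log(1 + count) together with its practice mean.

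Use this same window for closed- and open-cohort patients. A window of 12 months before the index result would not be safe for the open cohort. Those results fall between 4 October 2021 and 4 April 2022 (cancer-risk SAP 2.2), so up to six months of the window could lie after the trial start. Encounters in those months may already be affected by the program.

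Show the pre-trial encounter rate by arm in Table 2 of both SAPs, and report the model without the covariate as a sensitivity analysis. Both SAPs provide for a revised version in which the change can be recorded.

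The cost is some wording, two more coefficients and one more query, provided that pre-trial encounters can be extracted from the same EMR source. Patients with under 12 months of history need a stated rule, for example a new-patient indicator.
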